## I. Background and Significance

In the United States today only a small fraction of colonoscopies is performed without sedation. However, sedation is not routine across the globe, even among other developed countries. A recent study of colonoscopy practice in Italy reported that 45% of patients go without sedation. This number soars to 75% in Portugal and 82% in China. The use or lack of sedation does not alter the risks associated with the procedure; medication is only a matter of preference and comfort. Further research shows that time to reach the cecum is comparable in sedated and un-sedated patients, and discharge time is significantly shorter for un-sedated patients. Subjects in both groups were similarly willing to return to the same physician if a repeat colonoscopy was indicated. While the U.S. is a leader in sedated colonoscopies, there are increasing reasons for moving away from pharmacological analgesia.

In the midst of an opioid shortage projected to last into 2019, hospitals around the U.S. are searching for ways to conserve their dwindling drug supply for the patients most in need. As a significant percentage of colonoscopies worldwide are done without sedatives, and the use of sedation does not alter the associated risks, colonoscopy is an ideal procedure on which to try out alternative analgesics. Nearly 15 million colonoscopies are performed in the U.S. every year, and providing non-opioid pain-management options during these procedures has the potential to save huge quantities of medications, and help healthcare professionals effectively treat their patients during times of shortage.

While completely un-sedated colonoscopies are reported to be safe and well-tolerated among patients, there exist non-pharmacological methods of pain management that would confer the benefits of an un-sedated procedure, and possibly reduce patient pain perception and discomfort. One such method is the use of virtual reality (VR). This technology immerses the user in a virtual environment, and has been shown to have analgesic effects on patients undergoing procedures such as dental work and surgery done under local anesthesia. Burn wound care is a procedure that has been widely studied with patients using virtual reality. A within-subject study of both pediatric and adult burn patients found that the use of virtual reality during burn wound care significantly reduced perception of pain among participants. This decrease in pain perception was also seen in a recent Korean study, wherein virtual reality was used on patients during adductor canal catheter insertion. Subjects who received virtual reality during the procedure needed significantly lower doses of fentanyl and midazolam than the non-VR group, and reported overall lower levels of procedural pain.

Virtual reality may reduce perception of pain through distraction. Research has shown that in order to fully process nociceptor signals, the brain must focus attention on the pain itself. This claim is backed up with a large body of evidence showing that both adult and pediatric patients have a reduced perception of pain when using a variety of distraction methods. Subsequently, results reveal that the amount of attention directed towards pain is positively correlated with the level of pain experienced. Virtual reality technology provides users with an immersive experience on which to focus attention, leaving less available attention to direct towards pain.

## **II. Specific Aims**

The goal of this pilot study is to assess whether a virtual reality strategy is an acceptable alternative to pharmacological sedation during colonoscopy. We will collect data on patient willingness, tolerability, experience, and desire to use virtual reality during subsequent colonoscopy to draw a conclusion and make decisions about future research in this field.

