## **IV. Subject Enrollment**

Adult patients (over the age of 18) who have a scheduled screening or surveillance colonoscopy and have undergone at least one prior colonoscopy will be eligible for recruitment. The electronic medical record of the potential subject may be reviewed prior to contacting the patient to confirm eligibility status. Once a potential subject is identified, the patient will be sent a mailing which will outline the study, and request the opportunity for the research coordinator to contact them by phone regarding the study. This letter will provide the phone number of the research coordinator, and patients will be asked to contact the coordinator if they wish to participate. If the patient has not contacted the research coordinator two weeks after the letter has been sent, the coordinator will contact potential subjects by phone. A disclaimer on the letter will be included stating this. If the subject declines to take part in the

study, his/her name will be removed from the mailing list and they will not be contacted again regarding this research.

**Recruitment group:** Patient contacts research coordinator regarding study via phone

If the patient calls the research coordinator after receiving the letter in the mail, the coordinator will explain the study using a call script.

**Recruitment group:** Patient does not contact research coordinator after letter has been sent

If the patient does not contact the research coordinator following the mailing, the coordinator will contact him/her by telephone to explain the study using the call script and answer any questions. One phone call attempt will be made; if there is no response, the patient will not be contacted further.

All participants will be required to sign the written informed consent form on the day of the procedure.

The consent form will be pre-mailed to participants at their request.

**Patient recruitment targets:** This is a pilot study meant to assess effectiveness of a virtual reality approach to pain management. We aim to recruit 25 participants that are coming for routine screening or surveillance colonoscopies at MGH.

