Statistical Analysis Plan

Virtual Reality Alternative to Pharmacological Sedation During Colonoscopy

Principal Investigator

[name]

Director, High-Risk GI Cancer Clinic

Massachusetts General Hospital

Boston, Massachusetts

Protocol Identification Number

2018P001618

ClinicalTrials.gov identifier

[figure not shown]
NCT04349150

Statistical Analysis Plan

Virtual Reality Alternative to Pharmacological Sedation During Colonoscopy

Signature Page

Principal Investigator

[name]

9-22-2021

Date

1. Introduction

Virtual reality (VR) technology has been previously explored to reduce pain perception during medical procedures through distraction. We sought to determine whether VR technology may be a feasible alternative to pharmacological sedation during colonoscopy procedures.

2. Study design

Individuals 18 years or older who are scheduled for a routine colonoscopy and who have had a prior colonoscopy will be recruited to participate. The recruitment goal for this pilot study is 30 participants. Study participants will prep for the colonoscopy according to standard practice and will be prepared for the colonoscopy according to the standard of care at Massachusetts General Hospital. All participants will undergo a VR experience through a head-mounted display (HMD) throughout the duration of the colonoscopy and the procedure will be initiated without the administration of IV sedatives or narcotics. However, standard pain medication will be available upon participant request.

All participants will be asked to complete a questionnaire about their experience. The endoscopist will also complete a questionnaire about their experience working with the participant using VR distraction.

3. Aims and objectives

The goal of the study is to assess whether VR is an acceptable alternative to using pharmacological sedation during colonoscopy procedures. Data will be collected on participant willingness, tolerability, experience, and desire to use VR during subsequent colonoscopies.

4. Outcomes

4.1 Primary Outcome 1: Proportion of Individuals Who Complete Colonoscopy Using Virtual Reality and no Pharmacological Rescue

This outcome will be measured as x/n , where x = number of participants who completed colonoscopy using virtual reality and no pharmacological rescue, and n = total number of participants who initiated colonoscopy using virtual reality. This data will be collected immediately following the colonoscopy.

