4.4 Secondary Outcome 2: Participant Satisfaction

Participants will rate their satisfaction with their experience using virtual reality during colonoscopy on a numeric rating scale of 1-10 (1 = not satisfied, 10 = extremely satisfied). This data will be collected immediately following the colonoscopy.

4.5 Secondary Outcome 3: Participant Willingness to Undergo Future Colonoscopies With Virtual Reality and no Pharmacological Sedation

Participants will rate their willingness to undergo future colonoscopies using virtual reality and no-pharmacological sedation as "Yes," "Maybe," or "No." This data will be collected immediately following the colonoscopy.

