4.6 Secondary Outcome 4: Endoscopist Satisfaction

Endoscopists will rate their satisfaction performing colonoscopy on participants using virtual reality instead of pharmacological sedation on a numeric rating scale of 1-10 (1 = not satisfied, 10 = extremely satisfied). This data will be collected immediately following the colonoscopy.

4.7 Secondary Outcome 5: Endoscopist Willingness to Incorporate Virtual Reality Into Regular Colonoscopy Practice

Endoscopists will indicate whether they would incorporate VR into their regular colonoscopy practice by selecting one of the following: "Yes" "No" or "Yes, but I would use virtual reality as an adjunct therapy rather than a standalone therapy." This data will be collected immediately following the colonoscopy.

5. Populations to be analyzed

The population analyzed will consist of all participants who initiate the study using the virtual reality technology.

6. Analyses

6.1 Primary Outcome 1: Proportion of Participants Who Complete Colonoscopy Using Virtual Reality and no Pharmacological Rescue

This outcome will be analyzed as a percent from the proportion of participants who complete colonoscopy using VR and no pharmacological rescue.

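### Initial willingness to use VR is a stated aim without an outcome, and consented participants lost before the VR start are not counted in either primary proportion

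*Protocol*

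**What the plan says.** Protocol section II names four things to be measured: "We will collect data on patient willingness, tolerability, experience, and desire to use virtual reality during subsequent colonoscopy". SAP section 3 repeats them: "Data will be collected on participant willingness, tolerability, experience, and desire to use VR during subsequent colonoscopies". In both lists willingness comes first and the wish to use VR at a later procedure is a separate, final item.

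The SAP then defines two primary and five secondary outcomes. The only one about participants' willingness is SAP 4.5: "Participants will rate their willingness to undergo future colonoscopies using virtual reality and no-pharmacological sedation". It is answered Yes, Maybe or No, just after the procedure.

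For Primary Outcome 1 (SAP 4.1) the numerator is "x = number of participants who completed colonoscopy using virtual reality and no pharmacological rescue" and the denominator is "n = total number of participants who initiated colonoscopy using virtual reality". Primary Outcome 2 (SAP 4.2) has the same denominator. SAP section 5 says: "The population analyzed will consist of all participants who initiate the study using the virtual reality technology".

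On recruitment, protocol section IV says of a patient who declines that "his/her name will be removed from the mailing list and they will not be contacted again regarding this research". For those who do not reply to the letter: "One phone call attempt will be made; if there is no response, the patient will not be contacted further". Neither document plans a count of refusals, of patients not reached, or of reasons.

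**The concern.** The study is meant to show whether VR is an acceptable alternative to sedation and to guide further research. Two parts of that question come before the point where the SAP starts counting.

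The first is whether patients would try VR at all. This is the natural meaning of willingness once desire for later use is listed separately, and no outcome measures it.

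The second is what happens between consent and the start of the colonoscopy. Under protocol sections IV and V, consent is signed on the procedure day. Nursing preparation, the endoscopist's own consent and headset fitting in the procedure room follow. Someone who signs and then refuses the headset, or cannot bear it, has found VR unacceptable but appears in neither primary denominator.

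Followed exactly, the plan would report the same primary percentage whether nobody or several people were lost in that interval, and could not say how many of the patients reached chose to take part.

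**Working it through.** **Matching aims to outcomes**

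| Aim (protocol II, SAP 3) | SAP outcome |
|---|---|
| Willingness, initial | none |
| Tolerability | 4.1, 4.2, 4.3 |
| Experience | 4.3, 4.4 |
| Desire to use VR at a later colonoscopy | 4.5 |

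This allocation is my reading; the SAP does not map aims to outcomes. Sections 4.6 and 4.7 concern endoscopists. Assigning 4.5 to both the first and last rows would make the aim name one thing twice.

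**Who is counted**

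- Rescued or abandons VR after the start: stays in n and is a failure in Primary Outcome 1. With 25 starters, 3 such participants give 22/25 = 88%, and 6 give 19/25 = 76%. This part of the plan works.
- Consented, but refuses or stops VR before the start: not in n for 4.1 or 4.2.
- Fitted with the headset but stops before insertion: unclear. SAP 4.1 and 4.2 refer to initiating the colonoscopy, section 5 to initiating the study.
- Declined or not reached: in no analysis and no planned count.

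**Effect on Primary Outcome 1**

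The SAP gives no expected proportion, so there is no figure to reproduce. Let x be successes, n starters and w consented participants who refuse or stop VR before the start.

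- SAP: x/n
- All consented: x/(n + w) = (x/n) × n/(n + w)

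For x > 0 and w > 0 the second is always smaller. All values of x and w below are assumptions. The starter counts of 25 and 30 are the recruitment goals in protocol section IV and SAP section 2. Those goals disagree and need reconciling, but this point does not depend on which applies.

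| n | x | SAP x/n | w = 1 | w = 2 | w = 3 | w = 5 |
|---|---|---|---|---|---|---|
| 25 | 20 | 80% | 20/26 = 76.9% | 20/27 = 74.1% | 20/28 = 71.4% | 20/30 = 66.7% |
| 30 | 24 | 80% | 24/31 = 77.4% | 24/32 = 75.0% | 24/33 = 72.7% | 24/35 = 68.6% |

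If instead 30 is the number consented, w = 3 and x = 20, then n = 27. The SAP figure is 20/27 = 74.1%, against 20/30 = 66.7% over all consented, a gap of 7.4 percentage points.

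**What an uptake outcome could show**

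Exact (Clopper-Pearson) 95% intervals, with assumed numbers reached: 30/60 = 50% (36.8% to 63.2%) and 30/120 = 25% (17.5% to 33.7%). Even at pilot size these two situations are distinguishable, and the current outcomes would show neither.

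**The case against.** The strongest defence is that this is a small, single-arm, descriptive pilot with an openly stated denominator. Success among starters is a legitimate conditional quantity, and no passage applies it to everyone invited. The defence adds that the SAP speaks of participants' willingness, which 4.5 addresses in its own terms, and that the interval between consent and VR start is short.

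Much of this stands and limits the point. A reader might infer four stronger things that the documents do not support:

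- *Willingness is not measured at all.* SAP 4.5 does measure it, for future procedures among people who have tried VR. Only initial willingness lacks an outcome.
- *Early abandonment disappears generally.* It does so only before the start. Later abandonment is a failure in Primary Outcome 1, and protocol section V asks every subject for the questionnaire whether or not medication was requested.
- *Every denominator is affected.* SAP 6.7 counts endoscopists and states no denominator tied to VR starters. For mean pain and satisfaction scores, the direction of any effect is not established.
- *Completion multiplied by uptake gives the share of patients who find VR acceptable.* Not enrolling is not the same as refusing VR: some patients miss a single call, and others may decline research of any kind.

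The defence does not dispose of the two-item wording of the aim, which both documents carry, or of the gap between consent and start. A short interval makes losses less likely, but the plan has no place to record them if they occur.

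**Conclusion.** The point holds in a limited form. Initial willingness is a stated aim with no outcome. Consented participants who refuse or stop VR before the colonoscopy starts are left out of both primary proportions, and the two descriptions of initiation leave a borderline group unclassified.

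The existing Primary Outcome 1 is not wrong. It estimates tolerability among starters. A reader might conclude that the plan overstates acceptability as it stands; that follows only if the figure is applied to all those offered VR, which neither document does.

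The direction for Primary Outcome 1 is certain once pre-start refusals are classed as unsuccessful. The size cannot be derived, since the documents give no withdrawal or uptake figures. Under the assumed values above, with 80% success among starters, one to five pre-start withdrawals lower the proportion by about 3 to 13 percentage points. With no such withdrawals the two versions coincide. This is a worthwhile, inexpensive improvement and not a flaw that invalidates the study.

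**What to change.** 1. **Uptake.** Keep and report the numbers mailed, reached, not reached, declining, consenting and starting on VR. Where a patient offers a reason for declining, separate refusal of VR or of going without sedation from refusal of research. Report enrolled over reached, with an exact 95% interval, as a descriptive outcome labelled trial uptake.
2. **Supplementary Primary Outcome 1.** Keep the SAP 4.1 definition. Add a version over all consented participants, counting those who refused or stopped VR before the start as not successful. List separately the non-starts unrelated to VR, such as a cancelled procedure or equipment failure.
3. **One definition of initiation.** Use the same wording in SAP 4.1, 4.2 and 5, and say how to classify someone fitted with the headset who stops before insertion.

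The cost is a small amount of record keeping and a less favourable second figure if pre-start withdrawals occur. The counts must be kept on purpose: the protocol describes a call script but no call log, and removes decliners from the mailing list. A tally without names is enough.

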## **III. Subject Selection**

Inclusion criteria: Participants will be routine colonoscopy patients ages 18 years and over who have had a prior colonoscopy. Subjects of any race and gender will be recruited.

Exclusion criteria: Patients who are scheduled for monitored anesthesia care or general anesthesia will be excluded. Children (under 18 years) will be excluded because pediatric endoscopy patients receive general anesthesia at Massachusetts General Hospital.

First-time colonoscopy patients are excluded from the population to avoid the additional anxiety often experienced by patients undergoing this procedure for the first time. Virtual reality distraction depends largely upon the user allowing him/herself to turn attention to the virtual experiences and away from real experiences. Stressful situations, such as being in an unfamiliar medical environment awaiting an invasive procedure, activate the sympathetic nervous system. Sympathetic activation leads to hypervigilance – an active opponent of any distraction method. This pilot study will allow us to assess the effectiveness of this virtual reality pain management strategy in subjects who may not be as anxious, and allow us to determine whether the distraction method may be strong enough to reasonably offer it to first-time colonoscopy patients in future research.

All participants must be willing and able to provide written informed consent.

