6.2 Primary Outcome 2: Cecal Intubation Rate

This outcome will be analyzed as a percent from the proportion of participants in whom cecal intubation is achieved.

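### The plan promises a conclusion on whether VR is acceptable and a decision on future research, but reports each primary outcome as a bare percent with no interval and no progression criterion

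*Protocol*

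**What the plan says.** The aims call for a judgement as well as a description. Protocol II states: "The goal of this pilot study is to assess whether a virtual reality strategy is an acceptable alternative to pharmacological sedation during colonoscopy". The data are to be used "to draw a conclusion and make decisions about future research in this field". Protocol III adds a second decision, that the pilot will "allow us to determine whether the distraction method may be strong enough to reasonably offer it to first-time colonoscopy patients in future research". SAP 3 repeats the main aim: "The goal of the study is to assess whether VR is an acceptable alternative to using pharmacological sedation during colonoscopy procedures". SAP 1 words it as whether VR may be feasible in place of sedation.

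Protocol II also names the inputs: "We will collect data on patient willingness, tolerability, experience, and desire to use virtual reality during subsequent colonoscopy". The two primary outcomes, completion on VR without rescue and cecal intubation on VR without sedation, are defined only in SAP 4.1 and 4.2. Both are x/n, with n the participants who initiated colonoscopy using VR.

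The analyses are brief. SAP 6.1: "This outcome will be analyzed as a percent from the proportion of participants who complete colonoscopy using VR and no pharmacological rescue". SAP 6.2: "This outcome will be analyzed as a percent from the proportion of participants in whom cecal intubation is achieved". SAP 6.3 to 6.7 give means with standard deviations, one Pearson correlation and percentages for the secondary outcomes.

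Neither document gives a threshold, benchmark rate, confidence interval, test or progression rule. Neither says how the two primary outcomes combine with each other or with the patient-reported inputs.

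**The concern.** A conclusion about acceptability needs a standard, and a standard chosen once the percentage is known can be fitted to it. As written, two analysts who follow the SAP exactly could see the same completion percentage and reach opposite conclusions, both consistent with the plan. The decision on future research, including whether to offer VR to first-time patients, would then rest on a judgement made after the results.

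The missing interval compounds this. A percent from 25 or 30 people carries an uncertainty of about 20 percentage points either way, and the planned report would not show it.

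**Working it through.** **Inputs from the documents.** The recruitment target is 25 in Protocol IV ("We aim to recruit 25 participants that are coming for routine screening or surveillance colonoscopies at MGH") and 30 in SAP 2. Both primary outcomes are x/n among those who initiate with VR. The targets come without a null rate, target rate, alpha, power or precision goal, so neither can be reproduced. Both are carried through below, taking every recruited participant to initiate with VR.

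**Inputs that are assumptions.** The documents give no acceptable completion rate and no expected rate. Every true rate, cut-off and minimum level p0 below is illustrative.

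**Step 1: precision of a bare percent.** The two-sided exact (Clopper-Pearson) 95% interval for x of n runs from the 0.025 quantile of Beta(x, n − x + 1) to the 0.975 quantile of Beta(x + 1, n − x).

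| Observed | Percent | Exact 95% interval |
|---|---|---|
| 15/25 | 60% | 38.7% to 78.9% |
| 20/25 | 80% | 59.3% to 93.2% |
| 18/30 | 60% | 40.6% to 77.3% |
| 24/30 | 80% | 61.4% to 92.3% |

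The largest half-width over all possible x is 20.4 points at n = 25 and 18.7 points at n = 30.

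**Step 2: how much the unstated cut-off matters.** Let X be Binomial(30, 0.60), an assumed true completion rate of 60%. An observed cut-off c is met when X ≥ 30c.

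| Cut-off | Count needed | Probability of meeting it |
|---|---|---|
| 50% | 15 of 30 | 0.903 |
| 60% | 18 of 30 | 0.578 |
| 70% | 21 of 30 | 0.176 |
| 80% | 24 of 30 | 0.017 |

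The true rate is the same in every row. Moving the cut-off from 50% to 80% takes the result from a likely pass to a near-certain miss.

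**Step 3: what a strict criterion would cost.** Take as an example the rule that the one-sided 95% exact lower bound for Primary Outcome 1 must exceed p0 = 60%. The smallest passing count is the smallest r with P(X ≥ r | p = 0.60) ≤ 0.05. This is r = 20 of 25 (tail probability 0.029) and r = 23 of 30 (tail probability 0.044). The chance of passing is P(X ≥ r) at the true rate.

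| True rate | n = 25, r = 20 | n = 30, r = 23 |
|---|---|---|
| 70% | 0.19 | 0.28 |
| 80% | 0.62 | 0.76 |
| 90% | 0.97 | 0.99 |

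The rule is workable if the true rate is well above p0, and demanding if it is only 10 points above.

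**The case against.** The strongest reply is that this is a single-arm pilot with a purely descriptive SAP. The documents promise no test and no error rate, and their wording (assess, draw a conclusion, make decisions) allows a graded judgement over several inputs. That stands: a pilot does not need a hypothesis test, and a mechanical yes/no rule is more than the text requires. It does not remove the gap. A graded judgement also needs its grades, and the outcomes that feed them, stated before the data are seen.

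Three stronger readings are tempting, and the documents do not support them.

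- A reader might infer that the plan would accept even 0/n as showing VR acceptable. That is true only in the formal sense that no rule excludes it. Nothing suggests the investigators would say so, and the practical difficulty lies with mid-range results.
- A reader might infer that requiring the observed percent to reach the acceptable level is too lenient, because it is often met when the true rate only equals that level. A rate defined as acceptable should count as acceptable, so meeting the rule there is not an error. With an assumed level of 60%, a true rate of 50% meets that rule with probability 0.21 at n = 25 (15 or more) and 0.18 at n = 30 (18 or more). At a true rate of 40% the figures are 0.03 and 0.02. An informal rule therefore does discriminate, provided its level is fixed beforehand.
- A reader might infer that Primary Outcome 1 must decide alone, through a one-sided 5% test. Protocol II names patient-reported inputs for the conclusion, and the low pass probabilities near p0 in Step 3 make such a test a debatable choice for a pilot.

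It may also be too late to set a criterion. The SAP signature is dated 9-22-2021 and its introduction is in the past tense, but the documents do not say whether outcome data had been seen. The fix therefore has two branches.

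**Conclusion.** The concern holds in a limited form. The plan promises a conclusion on acceptability or feasibility and a decision on next steps, but supplies neither an interval for the primary proportions nor a criterion linking any outcome to that conclusion. The first part of the size needs no assumed true rate: at the stated targets the exact 95% half-width reaches about 19 to 20 points. The second part, probabilities from 0.90 down to 0.02 according to the cut-off, rests on an assumed true rate of 60%, n = 30 and a binomial model. It illustrates sensitivity and does not predict this trial's result.

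The finding does not mean that the trial is uninformative. It can estimate how often colonoscopy is completed on VR without rescue. What it cannot do as written is turn that estimate into an acceptability conclusion against a standard set in advance. The change should be made.

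**What to change.** 1. In SAP 6.1 and 6.2, report each primary proportion with a two-sided exact (Clopper-Pearson) 95% confidence interval. This applies in every case.
2. If outcome data have not been seen, add to SAP 3 a progression criterion that the sponsor fixes beforehand. State it as a proportion of those who initiate with VR. Name which outcomes govern, what happens if they disagree, and how the patient-reported inputs in Protocol II count. One option is a lower confidence bound for Primary Outcome 1 above a p0 chosen by the sponsor; graded criteria are another. Say whether the same criterion serves the first-time-patient decision in Protocol III.
3. If outcome data have been seen, reword Protocol II and SAP 1 and 3 to estimating the proportion who complete on VR without rescue. State that no acceptability or feasibility verdict will be drawn from the percentages alone, and bring the decision in Protocol III into line.
4. Reconcile the targets of 25 (Protocol IV) and 30 (SAP 2) before printing any criterion as a count.

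The cost is a few sentences, with no extra participants, data or procedures. The downside is that the trial can then miss its criterion, and a strict lower-bound rule would often do so if the true rate is only slightly above p0.
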